1.4. CONFIDENTIALITY

Participants will be assigned a unique identifier by the Sponsor. Any participant records or datasets that are transferred to the Sponsor will contain the identifier only; participant names or any information which would make the participant identifiable will not be transferred.

The participant must be informed that his/her personal study-related data will be used by the Sponsor in accordance with local data protection law. The level of disclosure must also be explained to the participant.

Medical information may be given to a participant's personal physician or other appropriate medical personnel responsible for the participant's welfare, for treatment purposes.

The participant must be informed that his/her medical records may be examined by Clinical Quality Assurance auditors or other authorized personnel appointed by the Sponsor, by appropriate IRB/IEC members, and by inspectors from regulatory authorities.

Study data may be submitted to government or other health research databases or shared with researchers, government agencies, companies, or other groups that are not participating in this study. These data may be combined with or linked to other data and used for research purposes, to advance science and public health, or for analysis, development, and commercialization of products to treat and diagnose disease. In addition, redacted clinical study reports and other summary reports will be provided upon request.

Confidentiality for Research Biosample Repository

Data generated from RBR samples must be available for inspection upon request by representatives of national and local Health Authorities, and Roche monitors, representatives, and collaborators, as appropriate.

Participant medical information associated with RBR samples is confidential and may only be disclosed to third parties as permitted by the Informed Consent Form (or separate authorization for use and disclosure of personal health information) signed by the participant, unless permitted or required by law.

Data derived from RBR sample analysis on individual participants will generally not be provided to study investigators unless a request for research use is granted. The

aggregate results of any conducted research will be available in accordance with the effective Roche policy on study data publication.

Genetic research data and associated clinical data may be shared with researchers who are not participating in the study or submitted to government or other health research databases for broad sharing with other researchers. Participants will not be identified by name or any other personally identifying information. Given the complexity and nature of these analyses, genetic data and analyses will not be shared with investigators or participants unless required by law.

Any inventions and resulting patents, improvements, and/or know-how originating from the use of the RBR sample data will become and remain the exclusive and unburdened property of Roche, except where agreed otherwise.

Monitoring and Oversight Research Biosample Repository

Samples collected for the RBR will be tracked in a manner consistent with Good Clinical Practice by a quality-controlled, auditable, and appropriately validated laboratory information management system, to ensure compliance with data confidentiality as well as adherence to authorized use of samples as specified in this protocol and in the Informed Consent Form. Roche monitors and auditors will have direct access to appropriate parts of records relating to participant participation in RBR for the purposes of verifying the data provided to Roche. The site will permit monitoring, audits, IRB/EC review, and Health Authority inspections by providing direct access to source data and documents related to the samples.

1.5. FINANCIAL DISCLOSURE

Investigators will provide the Sponsor with sufficient, accurate financial information in accordance with local regulations to allow the Sponsor to submit complete and accurate financial certification or disclosure statements to the appropriate Health Authorities. Investigators are responsible for providing information on financial interests during the course of the study and for one year after completion of the study (i.e., LPLV).

2. DATA HANDLING AND RECORD

2.1. DATA COLLECTION AND MANAGEMENT RESPONSIBILITIES

2.1.1. DATA QUALITY ASSURANCE

All participant data relating to the study will be recorded on printed or electronic CRF unless transmitted to the Sponsor or designee electronically (e.g., laboratory data). The Investigator is responsible for verifying that data entries are accurate and correct by physically or electronically signing the CRF.

The Investigator must maintain accurate documentation (source data) that supports the information entered in the CRF.

The Investigator must permit study-related monitoring, audits, IRB/IEC review, and regulatory agency inspections and provide direct access to source data documents.

The Sponsor or designee is responsible for the data management of this study including quality checking of the data.

Study monitors will perform ongoing source data verification to confirm that data entered into the CRF by authorized site personnel are accurate, complete, and verifiable from source documents; that the safety and rights of participants are being protected; and that the study is being conducted in accordance with the currently approved protocol and any other study agreements, ICH GCP, and all applicable regulatory requirements.

In addition, the Sponsor will implement a system to manage the quality of the study, focusing on processes and data that are essential to ensuring subject safety and data integrity. Prior to first subject entry into the study, the Sponsor will identify potential risks associated with critical trial processes and data and will implement plans for the control and review of these risks. Risk control includes the selection of risk-based parameters and establishing associated quality tolerance limits. Detection of deviations from defined quality tolerance limits will trigger an evaluation to determine if action is needed. Details on the management and review of quality tolerance limits will be provided in a separate Quality Tolerance Limit plan.

2.1.2. CLINICAL OUTCOME ASSESSMENT DATA

Not applicable.

2.1.3. SOURCE DATA RECORDS

Source documents (paper or electronic) are those in which participant data are recorded and documented for the first time. They include, but are not limited to, hospital records, clinical and office charts, laboratory notes, memoranda, evaluation checklists, pharmacy dispensing records, recorded data from automated instruments, copies of transcriptions that are certified after verification as being accurate and complete, microfiche, photographic negatives, microfilm or magnetic media, X-rays, participant files, and records kept at pharmacies, laboratories, and medico-technical departments involved in a clinical study.

Before study initiation, data to be entered directly into the eCRFs (i.e., no prior written or electronic record of the data) and considered source data must be defined in the Trial Monitoring Plan.

Source documents that are required to verify the validity and completeness of data entered into the eCRFs must not be obliterated or destroyed and must be retained per the policy for retention of records described below.

To facilitate source data verification, the Investigators and institutions must provide the Sponsor direct access to applicable source documents and reports for study-related monitoring, Sponsor audits, and IRB/EC review. The investigational site must also allow inspection by applicable Health Authorities.

2.1.4. USE OF COMPUTERIZED SYSTEMS

When clinical observations are entered directly into an investigational site's computerized medical record system (i.e., in lieu of original hardcopy records), the electronic record can serve as the source document if the system has been validated in accordance with Health Authority requirements pertaining to computerized systems used in clinical research. An acceptable computerized data collection system allows preservation of the original entry of data. If original data are modified, the system should maintain a viewable audit trail that shows the original data as well as the reason for the change, name of the person making the change, and date of the change.

2.2. RETENTION OF RECORDS

Records and documents, including signed ICF, pertaining to the conduct of this study must be retained by the Investigator for at least 15 years after study completion unless local regulations or institutional policies require a longer retention period. No records may be destroyed during the retention period without the written approval of the Sponsor. No records may be transferred to another location or party without written notification to the Sponsor.

2.3. STUDY RECORDS

The Investigator must maintain adequate and accurate records to enable the conduct of the study to be fully reconstructed, including but not limited to the protocol, protocol amendments, ICFs, and documentation of IRB/EC and governmental approval.

Roche shall also submit an Annual Safety Report once a year to the IEC and regulatory authorities according to local regulatory requirements and timelines of each country participating in the study.

2.3.1. Protocol Amendments

Any substantial protocol amendments will be prepared by the Sponsor. Substantial protocol amendments will be submitted to the IRB/EC and to regulatory authorities in accordance with local regulatory requirements.

Approval must be obtained from the IRB/EC and regulatory authorities (as locally required) before implementation of any changes, except for changes necessary to eliminate an immediate hazard to participants or any non-substantial changes, as defined by regulatory requirements.

2.3.2. Publication Policy

The results of this study may be published or presented at scientific meetings. If this is foreseen, the Investigator agrees to submit all manuscripts or abstracts to the Sponsor for approval prior to submission. This allows the Sponsor to protect proprietary information and to provide comments based on information from other studies that may not yet be available to the Investigator.

The Sponsor will comply with the requirements for publication of study results. In accordance with standard editorial and ethical practice, the Sponsor will generally support publication of multicenter trials only in their entirety and not as individual center data. In this case, a coordinating Investigator will be designated by mutual agreement.

Any formal publication of the study in which contribution of Sponsor personnel exceeded that of conventional monitoring will be considered as a joint publication by the Investigator and the appropriate Sponsor personnel.

Authorship will be determined by mutual agreement and in line with International Committee of Medical Journal Editors authorship requirements.

Any inventions and resulting patents, improvements, and/or know-how originating from the use of data from this study will become and remain the exclusive and unburdened property of the Sponsor, except where agreed otherwise.

2.3.3. Dissemination of Clinical Study Data

A description of this clinical study will be available at http://www.ClinicalTrials.gov.

2.3.4. Management of Study Quality

The Sponsor will implement a system to manage the quality of the study, focusing on processes and data that are essential to ensuring participant safety and data integrity. Prior study initiation, the Sponsor will identify and evaluate potential risks associated with critical trial processes and data and will implement controls for the communication, review and reporting of these risks. Details regarding the applied approach for the study will be provided in the integrated Risk Based Quality Management Plan.

Risk control includes the selection of risk-based parameters and establishing associated quality tolerance limits. Detection of deviations from defined quality tolerance limits will trigger an evaluation to determine if action is needed. Details on the management and

review of quality tolerance limits will be provided in a separate Quality Tolerance Limit plan.

2.3.5. Site Inspections

Site visits will be conducted by the Sponsor or an authorized representative for inspection of study data, participants' medical records, and eCRFs. The Investigator will permit national and local Health Authorities, Sponsor monitors, representatives, and collaborators, and the IRBs/ECs to inspect facilities and records relevant to this study.

3. ADMINISTRATIVE STRUCTURE

Internal Monitoring Committee (IMC) and Scientific Oversight Committee (SOC)

The IMC will perform periodic safety data review to ensure that continuation of the study does not pose a health hazard to participants, and review the results from the interim analyses to make decision about initiating new treatment arms.

IMC meetings will be scheduled following each of the planned interim analyses. Additional review meetings may be scheduled as determined by the IMC. Membership of the IMC will include representatives from Clinical Science (Translational Medicine), Clinical Safety, Biostatistics. If required, additional functional representatives may attend an IMC meeting.

A SOC will act as a consultative body to the Sponsor, providing external expert opinions on the safety data collected during the study. This committee will consist of an external group of at least two CHB therapeutic area experts who will advise the Sponsor on the interpretation of study data.

Data being evaluated by the SOC will include demographic, adverse event, serious adverse event, and relevant laboratory data. SOC may review efficacy data if safety concerns necessitate benefit-risk assessments. The Sponsor will retain all decision-making authority for this study.

Further details on the IMC and SOC, including membership, roles and responsibilities, are provided in the IMC and SOC Charter.

4. STUDY ARM, STUDY, AND SITE CLOSURE

The Sponsor (or designee) has the right to close a study site, terminate this study, study arms or certain NMEs in combination at any time. Reasons for terminating the study,

study sites, study treatment arms or certain NMEs may include, but are not limited to, the following:

- The incidence or severity of adverse events in this or other studies indicates a potential health hazard to participants.
- Participant enrollment is unsatisfactory.
- Emerging data and/or prioritization of assets.

The Sponsor will notify the Investigator and Health Authorities if the study is placed on hold, or if the Sponsor decides to discontinue the study or development program or terminate study arms or terminate certain NMEs in combination.

Study sites will be closed upon study completion. A study site is considered closed when all required documents and study supplies have been collected and a study-site closure visit has been performed.

The Investigator may initiate study-site closure at any time, provided there is reasonable cause and sufficient notice is given in advance of the intended termination.

Reasons for the early closure of a study site by the Sponsor or Investigator may include but are not limited to:

- Failure of the Investigator to comply with the protocol, the requirements of the IRB/IEC or local Health Authorities, the Sponsor's procedures, or GCP guidelines.
- Inadequate recruitment of participants by the Investigator.
- Discontinuation of further study treatment development.

Appendix 2 Adverse Events: Definitions and Procedures for Evaluating, Follow-up, and Reporting

1. DEFINITION OF ADVERSE EVENTS

According to the E2A ICH guideline for Good Clinical Practice, an **adverse event** is any untoward medical occurrence in a participant or clinical investigation subject administered a pharmaceutical product and which does not necessarily have to have a causal relationship with this treatment.

An adverse event can therefore be:

 Any unfavorable and unintended sign (including an abnormal laboratory finding), symptom, or disease temporally associated with the use of a medicinal product, whether or not considered related to the medicinal product.

Events Meeting the AE Definition:

- Deterioration in a laboratory value (hematology, clinical chemistry, or urinalysis) or other clinical test (e.g., ECG, X-ray) that is associated with symptoms or leads to a change in study treatment or concomitant treatment or discontinuation from study treatment (see Appendix 3, Section 4).
- Exacerbation of a chronic or intermittent pre-existing condition, including either an increase in frequency and/or intensity of the condition.
- New conditions detected or diagnosed after study treatment administration even though it may have been present before the start of the study.
- Adverse events that are related to a protocol-mandated intervention, including those that occur prior to assignment of study treatment (e.g., screening invasive procedures such as biopsies).
- "Lack of efficacy" or "failure of expected pharmacological action" per se will not be reported as an AE or SAE unless the progression is unexpectedly accelerated and not in line with the natural history of the disease. If the "Lack of efficacy" would not require safety reporting, such instances will be captured in the efficacy assessments. However, the signs, symptoms, and/or clinical sequelae resulting from lack of efficacy will be reported as AE or SAE if they fulfill the definition of an AE or SAE.

Events NOT Meeting the AE Definition:

Any clinically significant abnormal laboratory findings or other abnormal safety
assessments which are associated with the underlying disease, unless judged by
the Investigator to be more severe than expected for the participant's condition.

- The disease/disorder being studied or expected progression, signs, or symptoms of the disease/disorder being studied, unless more severe than expected for the participant's condition.
- Medical or surgical procedure (e.g., endoscopy, appendectomy): the condition that leads to the procedure is an AE.
- Situations where an untoward medical occurrence did not occur (social and/or convenience admission to a hospital).
- Anticipated day-to-day fluctuations of pre-existing disease(s) or condition(s) present or detected at the start of the study that do not worsen.

2. DEFINITION OF SERIOUS ADVERSE EVENTS

If an event is not an AE per definition above, then it cannot be a serious adverse event (SAE) even if serious conditions are met (e.g., hospitalization for signs/symptoms of the disease under study, death due to progression of disease).

A serious adverse event is defined as any untoward medical occurrence that at any dose:

- Results in death.
- Is life-threatening.

The term "life-threatening" in the definition of "serious" refers to an event in which the participant was at risk of death at the time of the event; it does not refer to an event which hypothetically might have caused death if it was more severe.

• Requires inpatient hospitalization or prolongation of existing hospitalization (see Appendix 3).

In general, hospitalization signifies that the participant has been detained (usually involving at least an overnight stay) at the hospital or emergency ward for observation and/or treatment that would not have been appropriate in the physician's office or outpatient setting. Complications that occur during hospitalization are AEs. If a complication prolongs hospitalization or fulfills any other serious criteria, the event is serious. When in doubt as to whether "hospitalization" occurred or was necessary, the AE should be considered serious.

Hospitalization for elective treatment of a pre-existing condition that did not worsen from baseline is not considered an AE.

Results in persistent or significant disability/incapacity

Disability means substantial disruption of the participant's ability to conduct normal life functions.

This definition is not intended to include experiences of relatively minor medical significance such as uncomplicated headache, nausea, vomiting, diarrhea, influenza, and accidental trauma (e.g., sprained ankle) which may interfere with or prevent everyday life functions but do not constitute a substantial disruption.

Is a congenital anomaly/birth defect.

Other significant events:

Medical or scientific judgment should be exercised in deciding whether SAE reporting is appropriate in other situations such as important medical events that may not be immediately life-threatening or result in death or hospitalization but may jeopardize the participant or may require medical or surgical intervention to prevent one of the other outcomes listed in the above definition. These events should usually be considered serious.

Examples of such events include

- elevated ALT or AST (> 3 × ULN and > 3x baseline) in combination with either an elevated total bilirubin (> 2 × ULN) or clinical jaundice in the absence of cholestasis or other causes of hyperbilirubinemia (Potential Hy's law).
- invasive or malignant cancers, intensive treatment in an emergency room or at home for allergic bronchospasm, blood dyscrasias or convulsions that do not result in hospitalization, or development of drug dependency or drug abuse.

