7. DEATHS

All deaths that occur during the protocol-specified adverse event reporting period (see Appendix 2, Section 5), regardless of relationship to study treatment, must be recorded on the Adverse Event eCRF and immediately reported to the Sponsor. This includes death attributed to progression of CHB.

Death should be considered an outcome and not a distinct event. The event or condition that caused or contributed to the fatal outcome should be recorded as the single medical concept on the Adverse Event eCRF. Generally, only one such event should be reported. If the cause of death is unknown and cannot be ascertained at the time of reporting, "unexplained death" should be recorded on the Adverse Event eCRF. If the cause of death later becomes available (e.g., after autopsy), "unexplained death" should be replaced by the established cause of death. The term "sudden death" should not be used unless combined with the presumed cause of death (e.g., "sudden cardiac death").

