10. HOSPITALIZATION OR PROLONGED HOSPITALIZATION

Any adverse event that results in hospitalization or prolonged hospitalization should be documented and reported as a serious adverse event (per the definition of serious adverse event in Appendix 2), except as outlined below.

An event that leads to hospitalization under the following circumstances should not be reported as an adverse event or a serious adverse event:

- Hospitalization for respite care
- Planned hospitalization required by the protocol (e.g., for study treatment administration or insertion of access device for study treatment administration)
- For administrative reasons (e.g., participant lives far away and is kept in the clinic/hospital for participant and/or site convenience)
- Hospitalization for a preexisting condition (not CHB), provided that all of the following criteria are met:
 - The hospitalization was planned prior to the study or was scheduled during the study when elective surgery became necessary because of the expected normal progression of the disease.
 - The participant has not suffered an adverse event.

An event that leads to hospitalization under the following circumstances is not considered to be a serious adverse event, but should be reported as an adverse event instead:

 Hospitalization for an adverse event that would ordinarily have been treated in an outpatient setting had an outpatient clinic been available.

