4.5.2 Adverse Events

Tables and listings will be presented with respect to;

- All clinical adverse events (AEs), summarized
- Serious adverse events (SAEs), and
- Adverse events of special interest (AESI)
 - Cases of elevated ALT or AST (> 3 × ULN and >3 × baseline) in combination with either an elevated total bilirubin (> 2 × ULN) or clinical jaundice (Potential Hy's law)
 - Suspected transmission of an infectious agent by the study treatment, as defined below:
 - Any organism, virus, or infectious particle (e.g., prion protein transmitting transmissible spongiform encephalopathy), pathogenic or non-pathogenic, is considered an infectious agent. A transmission of an infectious agent may be suspected from clinical symptoms or laboratory findings that indicate an infection in a participant exposed to a medicinal product. This term applies only when a contamination of the study treatment is suspected.
 - ALT or aspartate aminotransferase (AST) elevations ≥ 10 x ULN
 - Grade ≥3 hematology lab abnormalities (e.g., lymphopenia, neutropenia, leukopenia)
 - Severe/serious injection site reactions and/or injection reactions
- AEs will also be summarized by grade and causal relationship to the applicable study drug(s) part of the combination, as judged by the investigator
- AEs leading to dose interruptions or study drug adjustments
- Adverse events leading to withdrawal from the study treatment/study
- Listing of participants with Grade 2 blood cell count decreases or any infections Grade 2 intensity or higher.

The original terms recorded on the eCRF by the investigator for adverse events will be standardized by the sponsor. Reported AEs will be coded to preferred terms and body

systems as defined by the latest version of the Medical Dictionary for Regulatory Activities (MedDRA). Some AEs may be summarized by gender if required.

The adverse event severity grading scale for the DAIDS (v2.1) will be used for assessing severity for adverse events. For detail of the grading scale, please refer section 3.1 of the protocol.

Glossaries of the body systems, preferred terms and verbatim terms for all AEs and subgroups of AEs of special interest will be provided.

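### Appendix 2's examples of events that cannot be serious contradict Appendix 3 on deaths from chronic hepatitis B progression, and leave the status of relapse-related admissions ambiguous

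*Protocol*

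**What the plan says.** Protocol Appendix 2, Section 2 opens its SAE definition with a condition: "If an event is not an AE per definition above, then it cannot be a serious adverse event (SAE". The rest of that sentence illustrates what is ruled out: "even if serious conditions are met (e.g., hospitalization for signs/symptoms of the disease under study, death due to progression of disease". Whether the condition is met depends on Appendix 2, Section 1. That section removes from the AE definition the "expected progression, signs, or symptoms of the disease/disorder being studied, unless more severe than expected". The same section lists an exacerbation of a chronic pre-existing condition as an event that does meet the AE definition.

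Appendix 3 says the following:

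- **Section 7 (Deaths).** All deaths in the reporting period, "regardless of relationship to study treatment, must be recorded on the Adverse Event eCRF and immediately reported to the Sponsor". It adds: "This includes death attributed to progression of CHB".
- **Section 9 (Worsening of CHB).** Virological breakthrough, virological relapse and abnormal liver function tests are to be reported as AEs, with no severity condition. Other CHB deterioration is an AE only when the investigator judges the worsening unexpected.
- **Section 10 (Hospitalization).** An AE that leads to hospitalisation is an SAE under the Appendix 2 definition, apart from listed exceptions. One exception reads: "Hospitalization for a preexisting condition (not CHB), provided that all of the following criteria are met".

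Protocol Section 8.3.7 keeps ALT or AST rises below 10 × ULN with preserved hepatic function out of the standard AE process. SAP 4.5.2 lists "Serious adverse events (SAEs), and" among its outputs but gives no rule for CHB deaths or admissions.

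**The concern.** A site that handles a death from CHB progression finds it named in Appendix 2 as something that cannot be serious, and named in Appendix 3 as something that goes on the AE form and to the sponsor at once. A site that handles an admission for relapse faces a similar, less direct split.

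This is the kind of event the safety data most need to capture consistently. Participants who meet the Section 6.8 criteria stop NUC therapy. The Version 7 changes to follow-up monitoring were made to detect relapse early and prevent decompensation. SAE classification decides whether the event enters the SAE tables, the 24-hour SAE route and the SAE data given to the Scientific Oversight Committee.

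The effect may also differ between arms. Section 6.8 requires either HBsAg loss or a low HBsAg with a decline of at least 1 log10. Control HBsAg loss is assumed to be 3% (Section 9.2), whereas Appendix 9 reports that 60% of Phase 1 siRNA participants had HBsAg below 100 IU/mL. That is only one of the stopping conditions, but it suggests that stopping, and so relapse after stopping, would fall mostly in the experimental arms.

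**Working it through.** The plan states no figure on this point, so the check is a comparison of texts.

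**1. Death from CHB progression**

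- Appendix 2, Section 2 gives it as an example of a non-AE that cannot be an SAE.
- Appendix 3, Section 7 puts it on the AE form. That section treats death as an outcome and asks for the causal condition to be recorded as the event.
- A recorded AE with a fatal outcome meets the first seriousness criterion in Appendix 2, Section 2, which is the status the example denies.
- Section 7 does not use the term SAE, so SAE status is not settled in words. However, the 24-hour list in Appendix 2, Section 5 contains only SAEs, AEs of special interest, pregnancies, and accidental overdose or medication errors. A CHB death that is neither an SAE nor an AE of special interest has no route there for the immediate report that Section 7 demands.
- Result: a direct contradiction.

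**2. Admission for relapse, breakthrough or abnormal liver tests**

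- Appendix 3, Section 9 makes the underlying event an AE without a severity test.
- Appendix 3, Section 10 makes a hospitalised AE an SAE. Its pre-existing-condition exception leaves out CHB.
- The same admission fits Appendix 2's example of hospitalisation for the disease under study.
- Section 10 refers back to Appendix 2 for the definition, so it does not break the tie.
- Result: ambiguous. The answer depends on whether the AE test is taken from Appendix 2, Section 1 or from Appendix 3, Section 9.

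**3. Other CHB deterioration leading to admission**

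- Appendix 2, Section 1 and Appendix 3, Section 9 both turn on whether the worsening exceeds expectation.
- Result: no material conflict.

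**4. Abnormal liver tests alone**

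- Section 8.3.7 keeps ALT or AST rises below 10 × ULN with preserved function out of standard AE reporting.
- Appendix 3, Section 9 calls abnormal liver tests AEs and points to Section 8.3.8, where close monitoring starts above 3 × ULN.
- Result: rises between 3 and 10 × ULN with preserved function fall under both rules.

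**5. Scale only**

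- Input: about 30 participants per arm (Protocol Section 9.2).
- One reclassified event: 1/30 = 0.033, or 3.3 percentage points.
- Exact (Clopper-Pearson) 95% intervals: 0/30 gives 0 to 11.6%; 1/30 gives 0.1 to 17.2%. They overlap almost entirely, so one such event matters for its clinical content rather than for any formal comparison.
- The documents give no expected rate of CHB deaths or admissions, so the total effect on the SAE count cannot be computed.

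**The case against.** The strongest reply is that Appendix 2's sentence is conditional. It excludes only events that are not AEs, and Section 1 brings back disease events through the words "symptoms of the disease/disorder being studied, unless more severe than expected for the participant's condition". Entrants are virologically suppressed, with ALT no more than 1.5 × ULN and no significant fibrosis. A hospitalised flare, decompensation or CHB death in such a person would readily be judged worse than expected, and so could be an SAE under either appendix. This stands, and it defeats a stronger reading that a reader might infer from the examples alone: that Appendix 2 bars every CHB death and admission from being serious.

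A second inference also fails, namely that Appendix 3 requires every CHB admission to be reported. Section 10 starts from an event that is already an AE and defers to Appendix 2. Leaving CHB out of one exception does not by itself create a reporting duty.

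Nor would these events vanish from the safety output:

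- Section 7 sends deaths to the sponsor whatever their label.
- Potential Hy's law cases and ALT or AST at or above 10 × ULN are AEs of special interest with 24-hour reporting (Section 8.3.6).
- The SAP presents breakthrough and relapse by arm (4.5.3), and liver test abnormalities with an eDISH plot (4.5.3.1).
- The Scientific Oversight Committee sees AE and laboratory data as well as SAEs.

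The reply does not remove the conflict on deaths, because Section 7 carries no severity test. It also does not settle relapse admissions. The protocol itself anticipates relapse off treatment, so whether a given relapse exceeds expectation is a judgement for each investigator who knows the assigned arm. Death, ascites or encephalopathy without the special-interest laboratory values has no equivalent backstop.

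**Conclusion.** The text is wrong as written, within limits. On deaths attributed to CHB progression, Appendix 2's example contradicts Appendix 3, Section 7. On admissions for virological relapse, breakthrough or abnormal liver tests, SAE status is ambiguous. For other CHB deterioration the appendices agree in substance.

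The consequence is that SAE classification of a small but clinically important group of events can vary by site. The 3.3-point figure assumes an arm of about 30 and a single reclassified event, and is not an estimate of how often this will happen. The expectation that the effect would fall mainly on the experimental arms is an inference from the NUC stopping criteria and the Phase 1 HBsAg data, not something the documents state. The primary efficacy analysis is unaffected. The correction should be made because it is easy and the events concerned are serious.

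**What to change.** 1. In Appendix 2, Section 2, delete the parenthesis that holds the two examples.
2. State there that any death in the reporting period, including one from CHB progression, is recorded and reported as an SAE, with a reference to Appendix 3, Section 7.
3. State that hospitalisation for an event that Appendix 3, Section 9 classes as an AE is an SAE, subject to the exceptions already listed in Appendix 3, Section 10. A broader rule covering every CHB admission would override those exceptions and is not needed.
4. Reconcile Appendix 2, Sections 1 and 2 with Appendix 3, Sections 7, 9 and 10, and reconcile Protocol Section 8.3.7 with Appendix 3, Section 9 on abnormal liver tests.
5. Add one line to SAP 4.5.2 saying that these deaths and admissions are counted in the SAE tables.

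The cost is a few sentences in the protocol and one line in the SAP. The downside is that a few more events may be classed as SAEs.
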